6.4.4 Compliance and Adherence

The proposed medications are generally very well tolerated. Compliance with medication will be prompted periodically by SMS (text) messaging which we have utilised successfully in previous studies.

6.4.5 Concomitant Care

Concomitant care is permitted for study participants with the exception of other blood pressure lowering medications. The age of the study cohort together with the exclusion criteria reduces the likelihood of recruiting participants with concurrent chronic conditions.

6.4.6 Overdose of BP-Lowering Medication

Overdose of BP-lowering medication will be treated as a medical emergency. In this study treatment is open label. Normal NHS procedures for overdose will be followed in the unlikely event of overdose.

6.4.7 Protocol Treatment Discontinuation

In consenting to the trial, participants are consenting to blood pressure-lowering treatments, trial follow-up and data collection. However, an individual participant may stop treatment early or be stopped early for any of the following reasons:

- Unacceptable treatment toxicity or adverse event.
- Inter-current illness that prevents further treatment.
- Any change in the participant's condition that in the clinician's opinion justifies the discontinuation of treatment.
- Withdrawal of consent by the participant.

As participation in the trial is entirely voluntary, the participant may choose to discontinue treatment at any time without penalty or loss of benefits to which they would otherwise be entitled. Although not obliged to give a reason for discontinuing their treatment, a reasonable effort should be made to establish this reason, whilst remaining fully respectful of the participant's rights.

Participants who discontinue treatment, for any of the above reasons, should remain in the trial for the purpose of follow up and data analysis.

6.4.8 Intervention in the Observational Follow-up Study in the Low CASP Group.

The second stage of this study also incorporates a 12 month observational follow-up of the LOW CASP group (n=65) with repeat cMRI after 12 months. No medication will be administered to participants in the observational follow-up study as this represents 'usual care'. The observational follow-up study provides an opportunity to investigate whether there is any progression of cardiovascular structural change in patients with stage 1 hypertension who fall into in the LOW CASP group. The LOW CASP group will also serve as a reference against which the degree of regression in LVMI for the active intervention group of the RCT will be evaluated i.e. does BP-lowering regress LVMI to the level seen in those in the LOW CASP group? Concomitant medication will be allowed for participants in the observational follow-up study with the same stipulations as specified for participants in the RCT (see above).

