5.2.1 Explanation for choice of comparators

If this study demonstrates CASP to be a better predictor of left ventricular mass and therefore cardiovascular risk in young people than simple classification as stage 1 hypertension according to brachial BP, it follows that reducing CASP should regress left ventricular mass commensurate with a reduction in brachial BP. To investigate this, a randomised clinical trial will be undertaken in those identified to be in the highest quartile of CASP values from a cohort of people diagnosed with stage 1 hypertension. The active intervention will be BP lowering treatment, using anti-hypertensive treatments recommended by NICE guidance ⁽⁴⁾ and licensed for use in this age group – see section 6.4. The comparator is no treatment, which represents recommended usual care for patients with stage 1 hypertension and no other concurrent cardiovascular disease or overt target organ damage. These treatment regimens represent national guideline recommended approaches for the treatment of stage 1 hypertension in young people and are appropriate for use in this study. The use of no treatment as a comparator represents 'usual care' and avoids the unnecessary administration of placebo.

5.2.2 Study Hypotheses and Outcomes:

 We hypothesise that the non-invasive measurement of CASP will better define and stratify which younger people (18-54yrs) with stage 1 hypertension, according to their brachial BP, will have evidence of target organ damage as detected by MRI. We propose that those with the highest CASP values will have evidence of damage and are truly hypertensive, whereas those with the lowest CASP values will have no damage, are truly normotensive and are misclassified as hypertensive according to their brachial BP values.

- We hypothesise that the non-invasive measurement of CASP in younger people with stage 1 hypertension will better define who requires treatment. We propose that only those with high CASP values will have evidence of early cardiovascular structural damage and thus require treatment and that there will be no development of target organ damage in those with low CASP values if left untreated for 1 year.
- We hypothesise that those with high CASP values will exhibit evidence of pressure-mediated cardiovascular structural damage, and that this damage will regress with treatment targeted at reducing CASP for one year, confirming the benefits of treatment in those with high CASP values.

5.2.3 Key Research Questions:

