6.7 Sample Size

Two sample size calculations are presented for the TREAT CASP study; i) sample size to power the STOP/GO checkpoint; ii) sample size for the randomized clinical trial. As the sample size for the stage 2 RCT is critical for powering the study primary endpoint and because recruitment into the stage 1 screening study may be flexible to ensure sufficient recruitment, the sample size for the RCT is presented first.

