6.7.1 Sample Size for the Stage 2 Randomized Clinical Trial

The Primary Outcome Measure for the Stage 2 randomised clinical trial is the change in left ventricular mass index from baseline to study end between the intervention group (BP lowering) and the no treatment (usual care) group. No published data is available relating to the effects of treatment upon LV mass in young men without established cardiovascular disease. Therefore the sample size for the RCT (study stage 2) is based on an analysis of previously published data investigating the effects of BP lowering treatment on MRI-determined LV mass index (LVMI) in people with existing cardiovascular disease. Analysis of data taken from 4 individual treatment studies comprising 7 active treatment arms in 627 individuals, mean age 60±3.4 years (51-54), indicates an average difference in LVMI between treatments (treatment versus no treatment) of 6.6g/m², SD 10.9g/m² [Appendix, table 2]. All treatments in the cited studies used inhibitors of the renin-angiotensin system and achieved moderate reductions in blood pressure (average reduction with treatment -8/-4.5 mmHg). Based on an anticipated difference in LVMI between treatments of 6.6g/m², SD 10.9g/m², power calculations indicate a sample size of 58 people per treatment arm will be required to show a difference with 90% power at p=0.05 in LVMI between the treatment and no treatment groups for the RCT (study stage 2). Recruitment of 65 individuals per treatment arm will allow for 10% drop-out between treatments.

6.7.1.1 Justification for the specified duration of the RCT in stage 2.

The duration of the stage 2 RCT in the TREAT CASP study is 12 months. Prior studies of LVMI change in response to BP-lowering therapy indicate that the majority of LVMI regression occurs within the first 12 months of treatment with very little additional change with longer follow-up (up to 5 years), ^(55,56). This is because LVMI regression is powerfully determined by the extent of the reduction in BP on treatment, and the BP change is maximal during the first year of therapy. Thus, the anticipated change in BP with treatment and the proposed study duration has been chosen to maximise the change in LVMI within a reasonable timescale for the RCT.

6.7.2 Sample size underpinning the STOP/GO check point at the end of the stage 1 Screening Study

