The inbuilt STOP/GO checkpoint to allow the study to proceed to the RCT (stage 2) is based on achieving a significant difference in LVMI as measured by MRI between people in the HIGH CASP and LOW CASP groups at the end of the screening phase (stage 1 see section 6.3.1.7).

Previously published studies indicate that LVMI is directly related to blood pressure and that the relationship between the change in systolic blood pressure and the change in LVMI approximates to the order of $1g/m^2$ LVMI per mmHg SBP ^(57,58). This order of magnitude of change is similar to that seen for the regression in LVMI with BP-lowering treatment in the analysis of published studies for the RCT power calculation (average reduction in SBP -8 mmHg, average reduction in LVMI with treatment -6.6 g/ m^2). Preliminary data from our clinical laboratory in men with stage 1 hypertension stratified by their CASP values indicates that groups incorporating the highest and lowest 25% of the population with regard to their CASP values are separated by brachial systolic blood pressures of at least 10mmHg [Appendix, figure 7]. Based on the relationship between LVMI and BP as outlined above, this indicates a likely separation between groups in LVMI of approximately $10g/m^2$. With regard to a starting value, systematic review of LVMI values by MRI in 1,032 young men from 11 published studies indicates a mean value of 78.5 g/m², SD 11.8g/m² ($^{59-67}$). Combining an estimated 10g/m² difference between the HIGH and LOW CASP groups with the SD for LVMI in young men, indicates a sample size of 31 per group would be required to demonstrate a difference in LVMI with 90% power at p=0.05. This indicates that a sample size of 65 individuals in the LOW CASP and 130 individuals for the HIGH CASP group should have abundant power to demonstrate a difference in LVMI at the study STOP/GO checkpoint. This will provide a robust basis to confirm or refute our hypothesis that CASP provides an effective mechanism for identifying patients with and without pressure-related target organ damage, in people with a diagnosis of stage 1 hypertension.

6.7.2.1 Consideration of variability in LVMI:

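### The LOW CASP cohort of 65 has no margin or precision target, so a non-significant change would not establish non-progression, and a HIGH v LOW difference cannot show that LOW CASP men are undamaged

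*Protocol*

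**What the plan says.** The second hypothesis in section 5.2.2 is that "there will be no development of target organ damage in those with low CASP values if left untreated for 1 year". The first hypothesis there adds that men with the lowest CASP are undamaged and wrongly labelled as hypertensive. Section 6.4.8 says that stage 2 "incorporates a 12 month observational follow-up of the LOW CASP group (n=65) with repeat cMRI after 12 months". It gives the cohort two uses: to see whether structure progresses without treatment, and to serve as a reference for the treated arm, asking "does BP-lowering regress LVMI to the level seen in those in the LOW CASP group".

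Section 6.7 states that "Two sample size calculations are presented for the TREAT CASP study", one for the randomised comparison and one for STOP/GO. The LOW group enters only the second (6.7.2), where 65 LOW and 130 HIGH men are judged ample against a requirement of 31 per group. Sections 6.3.1.9 and 6.7.2 then say that this comparison will confirm or refute whether CASP separates men with pressure-related damage from men without it. Section 6.10.4.2.3 makes it a t-test at P<0.05.

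**The concern.** A hypothesis of no change is not supported by failing to find a change. It needs a largest change that would still count as none, and a cohort able to exclude anything larger. The protocol gives neither, and it fixes the cohort size on a different question. The same holds for any statement that treated men have come down to the LOW level.

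The STOP/GO conclusion has a different fault. Under 6.3.1.2 all participants have stage 1 hypertension, and HIGH and LOW are the two ends of that one distribution. A difference between them says which end has the higher LVMI. It does not place the lower end against people without hypertension.

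At stake is one of the benefits listed in 5.1.8.1: that men with a normal CASP could be spared treatment because they show no damage at baseline or at 12 months.

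**Working it through.** **Inputs**
- LOW cohort 65 (6.4.8). Completers: 65 × 0.90 = 58.5, taken as 58, under the randomised trial's 10% allowance (6.7.1); 65 × 0.95 = 61.75, about 62, under the loss of below 5% expected in 6.10.2.2.
- SD of LVMI change: 10.9 g/m² (6.7.1, averaged over treated arms) or 6.7 g/m² (Appendix Table B, from 12 placebo patients).
- Untreated change: a rise of 2.0 g/m² (Appendix Table B, 12 + 15 = 27 patients). The table signs falls as positive, so its -2.0 is a rise; the usual-care row goes from 77.0 to 79.0.
- Baseline HIGH minus LOW gap 10 g/m² and cross-sectional SD 11.8 g/m² (6.7.2); fall on treatment 6.6 g/m² (6.7.1 and Appendix Table A).

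**1. The protocol's own sizes.** n per group = 2 × (SD/difference)² × (1.96 + 1.2816)².
- Randomised trial: 2 × (10.9/6.6)² × 10.51 = 57.3, so 58; 58/0.90 = 64.4, so 65. Reproduced.
- STOP/GO: 2 × (11.8/10)² × 10.51 = 29.3, so 30; the t-based value is 30.25, so 31. Reproduced.

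The arithmetic is sound. Both sizes answer questions about detecting a difference.

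**2. Change in untreated LOW men.** Half-width = t × SD/√n. The miss rate is 1 minus the power of a two-sided one-sample t-test at 0.05 for a true rise of 2.0 g/m².

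| n | SD | 95% half-width | Rise of 2.0 missed |
|---|---|---|---|
| 65 | 6.7 | 1.66 | 34% |
| 62 | 6.7 | 1.70 | 36% |
| 58 | 6.7 | 1.76 | 39% |
| 65 | 10.9 | 2.70 | 69% |
| 62 | 10.9 | 2.77 | 70% |
| 58 | 10.9 | 2.87 | 72% |

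For a rise of 1 g/m² the miss rate is 78-89% over the same range.

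**3. Treated HIGH v LOW at 12 months.** If LOW does not change, the planning figures leave 10 − 6.6 = 3.4 g/m². Half-width = 1.96 × 11.8 × √(2/n): 4.06 at 65 per group, 4.29 at 58. Two-sample t-test power for 3.4 is 37% and 34%, so a non-significant result occurs in 63% and 66% of trials. If LOW itself rose by 2.0, the gap would be 1.4 and non-significance about 90%.

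**4. What a margin would ask of the LOW cohort.** The protocol names none, so 2 g/m² is only an illustration. With a true change of zero and one-sided 0.025, n = (SD × (1.96 + z)/2)²: 89 (80% power) or 118 (90%) at SD 6.7; 234 or 313 at SD 10.9. With 65 men the power is 67% or 31%.

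**5. The STOP/GO inference.** The t-test contrasts mean LVMI in two hypertensive groups. The mean of 78.5 g/m² for young men in 6.7.2 is a planning value; no comparison with it is laid down. Rejecting the null gives a mean difference and nothing about whether LOW is at a normal level.

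**The case against.** The strongest reply is that the protocol does not commit the error. Section 6.4.8 puts a question and calls LOW a reference; that is compatible with an estimate and interval. Regression to the LOW level is not a hypothesis: the third one in 5.2.2 says only that damage will regress. Section 5.1.8.2 openly allows that LOW men may progress and says what that would mean. Margins for a secondary, non-randomised comparison may also sit in an analysis plan that is not shown, and the t-tests above are this review's choice, since 6.10.4.2 names mixed models.

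Much of this stands. A reader might infer that the protocol will read non-significance as no difference, so that normalisation would be wrongly declared in about 66% of trials. The documents do not support that: only STOP/GO (6.3.1.9) equates failing to reject with no difference. Nor do the planning figures prove that full regression would be false. The gap of 10 is approximate, the 6.6 comes from patients averaging 60 years with existing disease, and LOW is assumed stable. A missed rise in LOW is not the likelier outcome at every SD either: at 6.7, a rise of 2.0 is detected in 61-66% of trials.

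What remains does not depend on the analysis plan. The absence hypothesis and the figure of 65 are fixed in this protocol, as is the statement of what STOP/GO will confirm. Baseline adjustment would sharpen the HIGH v LOW comparison, but no baseline-to-12-month correlation is given to say by how much.

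**Conclusion.** The point holds as a limit on what may be concluded. Non-progression in LOW is framed as an absence, while the cohort can estimate the change only to within about 1.7-2.9 g/m². If the true rise were 2.0 g/m², 34-39% of trials (SD 6.7) or 69-72% (SD 10.9) would show no significant change, so such a result could not establish non-progression. The 2.0 is an assumption carried over from older cardiac patients, and each SD has a weak basis for young men.

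For the question in 6.4.8, a residual of about 3.4 g/m² (LOW assumed stable) is smaller than the 4.1-4.3 g/m² half-width, so non-significance would not show regression to the LOW level.

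Independently of any of these figures, the STOP/GO test can show only that LVMI is higher in HIGH than in LOW. Severity is low, because the randomised primary comparison is untouched.

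**What to change.** 1. In 5.2.2, conclude non-progression in LOW only if the upper 95% confidence limit for 12-month LVMI change lies below a margin fixed before the 12-month data are seen; otherwise report the estimate and interval alone. The choice of margin should allow for the half-width: with a margin at or below it, the claim could be made only if the observed change were a fall.
2. State that treated HIGH v LOW at 12 months will be reported as an estimate with a 95% CI, and that non-significance will not be taken as normalisation.
3. In 5.2.2, 6.3.1.9 and 6.7.2, restrict the STOP/GO conclusion to higher LVMI in HIGH than in LOW, and remove absence of damage and true normotension from what that test is said to confirm.

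The cost is wording and interval-based reporting, with no extra participants or visits. The downside is a weaker claim from the LOW cohort.

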6.5 Outcomes

6.5.1 Primary Outcome

THE PRIMARY OUTCOME for the TREAT CASP study is the change in left ventricular (LV) mass index from baseline to study end (12 months) in the randomised clinical trial comparing active treatment vs. no treatment. The primary outcome will be evaluated using 1.5T Cardiovascular MRI and will be expressed as grams per metre squared. Evaluation of the primary endpoint will be blind to treatment allocation. cMRI is the preferred mode of evaluation because of its excellent reproducibility, allowing adequately powered studies, with much reduced sample size and greater precision than echocardiography. Detail regarding measurement of the primary outcome variable is shown in section 6.10.1.

6.5.2 Secondary Outcomes

Secondary outcomes in the TREAT CASP study are designed to evaluate mechanisms exploring the relationship between CASP vs. conventional brachial BP on extended markers of cardiac and vascular damage both in cross-sectional evaluations at the end of the STAGE 1 screening study and in longitudinal analysis during STAGE 2, after 12 months follow-up of the LOW CASP observational cohort and the HIGH CASP RCT.

Secondary outcomes for the TREAT CASP study will be:

- 1. LV mass/volume ratio;
- cMRI myocardial tissue tagging to demonstrate alterations in regional systolic and diastolic strain – early markers of hypertension-mediated damage;
- cMRI measurement of interstitial fibrosis using T1 mapping marker of damage as a prelude to impaired function;
- 4. cMRI measures of aortic distensibility and pulse wave velocity sensitive indices of aortic stiffening. This tests our subsidiary hypothesis that increased aortic stiffness causes the detrimental increase in CASP relative to brachial BP;
- 5. High resolution cMRI spin echo sequences to measure carotid and aortic wall thickness;
- 6. Albumin excretion rate (Urinary Albumin: Creatinine ratio) as an index of early renal injury;
- 7. Retinal photography to document hypertensive changes in retinal small vessels.

Detail regarding measurement of the secondary outcome variables is shown in section 6.10.1.

6.6 **Participant Timeline**

Participants in the TREAT CASP study will initially be recruited into the stage 1 screening study. Stage 1 screening study recruitment will remain on-going from study commencement (mid 2013) until 500 participants have been screened (~18 months). At this time, data from the stage 1 screening study will be collated and used to stratify participants into the upper and lower quartiles based upon their CASP values (HIGH and LOW CASP groups). Only those participants falling into the HIGH and LOW CASP groups will then be invited to return to the research centre to undergo cardiac MRI. Once participants in the HIGH and LOW CASP groups have undergone cMRI, the STOP/GO checkpoint will be evaluated (early 2015) to dictate whether the study proceeds to the second stage (stage 2 RCT and observational follow-up study). The study assessments in the stage 1 screening study have already been described (section 6.3.1.7) and are shown in the schedule of assessments below.

If the study proceeds to the second stage, those stage 1 participants identified as constituting the HIGH CASP group will then be invited to participate in the randomised clinical trial (n=130, early 2015). At the same time, 65 participants from the LOW CASP group will be invited to participate in the observational follow-up study. Participants entering the randomised clinical trial will commence medication at randomisation, i.e. there is no need for a wash-out/run-in period as this is a trial in treatment naïve participants. Similarly, those entering the observational follow-up study will be entered immediately at their randomisation visit.

For people participating in either the stage 2 randomised clinical trial or the stage 2 observational follow-up study, the study measurements performed during the stage 1 screening study (except for documentation of medical/lifestyle history and physical examination, see section 6.3.1.7) will be repeated both at randomisation (baseline) and at study end (study close out, 12 months). Ambulatory blood pressure monitoring will also be performed at randomisation and study end for all participants in the stage 2 randomised clinical trial and the observational follow-up study. All ABPM measurements during the stage 2 randomised clinical trial and observational follow-up study however, will use a wrist-mounted device (BPro device, Healthstats, Singapore) rather than the arm cuff device (Spacelabs) used in the Stage 1 screening study. This is because the wrist-mounted BPro device allows simultaneous monitoring of both brachial and central blood pressure over the course of 24 hours (see section 6.10.1) and will be used to monitor the change in 24-hour ambulatory blood pressure over the RCT and the observational follow-up studies.

In addition to the visits planned at randomisation and study end, all participants in either the stage 2 randomised clinical trial or the observational follow-up study will be asked to return to the research centre 3 and 6 months following randomisation for measurement of their seated brachial BP and CASP and to document any adverse events. For participants in the stage 2 randomised clinical trial, further study visits will be scheduled for the actively treated group only, i.e. within the first 4 months and at 9 months, to optimise and up-titrate treatment as necessary and to ensure that the actively treated cohort in the randomised clinical trial achieve and maintain their CASP target for at least 8 months during follow-up. The schedule of study visits and study assessments in the TREAT CASP study is shown in the table below.

Participants not entering the stage 2 randomised clinical trial or observational follow-up study will complete the study following their stage 1 screening visit or their first cMRI visit and will be discharged from the TREAT CASP study.

Visit	1	2	3	4	5	6	7	8	9	10
Туре	Screening	MRI	Randomisation	Safety	Follow-	Follow-	Follow-	Follow-up	Follow-	Close-
	*	1	-		up	up	up	••	up	out
Week			0	4	8	12	16	26	38	52
Study Stage	1	1	2	2	2	2	2	2	2	2
PROCEDURE										
Signed Informed Consent	х		х							
Medical History	х									
Physical Exam	х									х
Seated Brachial BP	х		х	X	Х	х	X	х	X	х
CASP	х		х	X	Х	х	X	х	X	х
Height/Weight	х		х							х
Body Fat Composition	х		х							х
(Bio-impedance)										
Full Blood Count	х		х							х
Clinical Chemistry	х		х	X						х
Non Fasting/Fasting Glucose	x		х							х
Urinary Albumin:Creatinine	х		х							х
Ratio										
Urine Dip-Stick Test	х		х							х
ECG	х		х							х
24-Hour brachial ABPM	х									
(Spacelabs)										
24-Hour central ABPM (BPro)			х							х
Non-Mydriactic Retinal			х							х
Photography										
SF-36 QoL Questionnaire			х							х
Dispense Study Meds			x	X	X	X	X	x	X	х
Document Adverse Events			х	X	X	х	X	х	X	х
MRI		х								х

TREAT CASP Study Schedule of Visits and Assessments

Text in blue indicates treatment group (1) only.

*Screening visits occur in first study year (Stage 1), prior to Stop / GO checkpoint for the subsequent RCT (Stage 2)

¶ MRI visits occur within 3 months of subsequent randomisation

Both the randomised clinical trial and the observational follow-up study will be carried out over a 12 month period, with additional study visits scheduled during this period (see schedule of assessments, section 6.10). A repeat cMRI will be performed at the end of 12 month period (final visit, January-March 2016).

